5.2 Baseline Assessment (Visit 1, Week 0)

At the time of baseline, the coordinator will document the following:

- Vital signs (weight, temperature, blood pressure, heart rate, respiratory rate, pulse oximetry)
- Physical exam including general appearance, HEENT, cardiovascular, pulmonary, abdominal, neurologic, dermatologic, and musculoskeletal exams
- Current medications
- Safety blood work for renal and liver evaluation
 - AST, ALT, AP, total bilirubin, creatinine
- Review bronchoscopy results (if performed)
- ECG
- Perform spirometry
- Undergo an HRCT scan with inspiratory and expiratory image acquisition (if HRCT was not done in preceding 6 weeks)
- Serum pregnancy test (if applicable)
- Review adverse events

5.3 Visits 2, 3, 5, 6 (Weeks 4, 8, 16, 20): may be performed at study center or by local lab draw in conjunction with phone visit

- Safety labs to monitor renal and liver function AP, ALT, AST, total bilirubin, creatinine
- Review hospitalizations
- Review medication compliance
- Review concomitant medications
- Review adverse events

5.4 Visit 4 (Week 12):

- Vital Signs (weight, temperature, blood pressure, heart rate, respiratory rate, pulse oximetry)
- Physical exam including general appearance, HEENT, cardiovascular, pulmonary, abdominal, neurologic, dermatologic, and musculoskeletal exams
- Safety blood work for renal and liver evaluation
 - o AP, ALT, AST, total bilirubin, creatinine
- Spirometry
- ECG
- Review hospitalizations
- Review medication adherence
- Review concomitant medications
- Review adverse events
- 5.5 Visit 7 (Week 24):
 - Vital Signs (weight, temperature, blood pressure, heart rate, respiratory rate, pulse oximetry)
 - Physical exam including general appearance, HEENT, cardiovascular, pulmonary, abdominal, neurologic, dermatologic, and musculoskeletal exams Safety blood work for renal and liver evaluation

- o AP, ALT, AST, total bilirubin, creatinine
- Spirometry
- ECG
- HRCT scan
- Review hospitalizations
- Review medication adherence
- Review concomitant medications
- Review adverse events
- Collect unused study medication and return to investigational pharmacy
- Bronchoscopy with consent of patient and primary physician if no contraindication identified

5.6 Visit 8 (Week 28) (Phone visit):

At the 28 week phone visit, the coordinator will:

- Review hospitalizations
- Review adverse events
- Collect vital status

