2. BACKGROUND/RATIONALE/PRELIMINARY STUDIES

Our principle hypothesis is that pirfenidone therapy will stabilize lung function decline and slow progression of fSAD in lung transplant recipients with CLAD.

Greater than 50% of lung transplant recipients show signs of CLAD by 5 years posttransplantation (1). This process arises from development of graft fibrosis in a peri-bronchial (bronchiolitis obliterans or BO), peri-vascular, or fulminant interstitial and airway luminal fibrosis distribution (2, 3). Therapies to prevent or slow CLAD are lacking. Anti-fibrotic therapies may offer an avenue to prevent progression of CLAD and prolong allograft survival.

Pirfenidone, an oral anti-fibrotic agent, was approved for treatment of idiopathic pulmonary fibrosis (IPF) in 2014. In large multi-center, international clinical trials, pirfenidone has been shown to reduce the rate of FVC decline in patients with IPF with a favorable safety and tolerability profile (4, 5).

Small airways, the predominant histologic target of fibrotic remodeling in a chronically rejecting lung allograft, have been termed the "silent zone" of the lung secondary to difficulty in evaluating this disease process by pathology or imaging (6). While high resolution CT (HRCT) scans are routinely obtained at CLAD onset, HRCT findings in CLAD lack specific diagnostic features, and small airways cannot be visualized or evaluated by standard methods.

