A novel imaging technology to evaluate functional small airways disease (fSAD) has been developed and validated at the University of Michigan. This technology, termed parametric response mapping (PRM), utilizes voxel by voxel comparison of inspiratory and expiratory HRCT images through co-registration to provide quantitative measures of fSAD. This tool has been utilized in patients with a variety of lung diseases including patients with chronic obstructive pulmonary disease (COPD) and lung transplant recipients (7-9). Higher levels of fSAD in lung transplant recipients with CLAD has been associated with decreased survival, and fSAD values have been shown to increase over time compared to transplant patients without chronic rejection (8, 9). We propose to utilize this novel imaging biomarker to track the change in fSAD, as it relates to change in traditional measures of FEV₁ or FVC, in patients with CLAD enrolled in this clinical trial. We have significant experience in longitudinal monitoring of lung function and have been pioneers in describing the natural history of spirometric decline after CLAD onset (10). Imbio Platform systems, a commercial company with quantitative image biomarker algorithms, will be utilized in this study.

Furthermore, this study will employ a novel biological biomarker of fibroproliferation, mesenchymal stromal cells (MSCs), in assessing the effect of pirfenidone on CLAD. Use of this biomarker is based on 10 years of work in our lab demonstrating that MSCs can be isolated from BAL of lung transplant recipients and are biomarkers of BOS (11, 12). The number of MSCs can be quantitated by a colony forming assay and now as a nested PCR based mRNA measure of unique lung-MSC transcription factors Foxf1 (11). The third aim of this study will investigate the effect of pirfenidone on MSC number and phenotype. This will be the first study analyzing novel imaging and MSC biologic markers of fibroproliferation following administration of a therapeutic agent for CLAD.

Schematic of Study Design

Prior to Enrollment

Obtain informed consent. Screen potential subjects by inclusion and exclusion criteria; obtain medical history; HCRT, BAL (optional), vital signs, EKG, spirometry, pregnancy test (if applicable), concomitant medications, Adverse events from time of signing consent.

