4.4 EXCLUSION CRITERIA

- Acute Rejection (AR) diagnosis by biopsy in the 28 days prior to enrollment
- Treatment with pulse steroids, Anti-thymocyte Globulin (ATG), extracorporeal photopheresis (ECP), plasmapheresis, or Immunoglobulin therapy aimed at CLAD within the 28 days prior to enrollment
- If the subject is receiving chronic Azithromycin therapy, the dose must be stable for the 28 days prior to enrollment
- Presence of active pulmonary infection at the time of enrollment as determined by an investigator in consultation with the treating pulmonologist
- Diagnosis of bronchial stenosis either a) requiring stenting, or b) thought to be responsible for the spirometric decline by principal investigator
- Abnormal liver function tests (AST or ALT > 2 x upper limit of normal (ULN), Alkaline phosphatase > 2.5 x ULN, total bilirubin > ULN) or known cirrhosis (>2 times upper limit of normal of AST/ALT/AP)
- Total WBC < 3.0 K/uL
- Moderate to Severe Renal insufficiency (CrCl <15 mL/min calculated by the Cockcroft-Gault equation)

- Use of any medication known to cause significant interactions with pirfenidone (strong CYP1A2 inhibitors such as Fluvoxamine or Enoxacin or inducers)
- Pregnancy or lactation. Women of child-bearing potential will have a pregnancy test at enrollment and must agree to maintain highly effective contraception with two methods of birth control from the date of consent through the end of the study.
- Tobacco use within 6 months
- History of alcohol abuse in the past 1 year as determined by the treating pulmonologist
- Any condition other than CLAD that will likely result in death in the next 1 year
- Any condition in the judgement of the principal investigator that would preclude participation in this study
- EKG with QTc interval > 500 msec at screening
- Listed for repeat lung transplantation

Excluded therapies:

The following therapies are not permitted during the study:

- Investigational therapy, enrollment in another therapeutic clinical trial within 30 days or 5 half-lives of study medication (whichever is longer)
- Fluvoxamine

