5.0 STUDY VISITS

5.1 Screening

Lung transplant recipients at the University of Michigan will be screened by the study team for participation in this trial. If deemed eligible, subjects will be approached regarding study, and the consent form as well as inclusion and exclusion criteria will be reviewed.

Screening Visit (Performed up to 6 weeks prior to baseline visit and initial study drug dosing) The following procedures will be completed at screening:

- Obtain and document informed consent
- Obtain sex, race, ethnicity, date of birth
- Vital signs (height, weight, temperature, blood pressure, heart rate, respiratory rate, pulse oximetry)
- Review medical history, including transplant history
- Review current medications
- Date of spirometric decline (defined as date of first spirometric measurement used to document spirometric decline) and CLAD phenotype
- Review of bronchoscopy results (if performed in the 6 weeks prior to screening visit)
- Blood draw for screening labs
 - AST, ALT, AP, total bilirubin, creatinine

Screening Bronchoscopy

Bronchoscopy is often employed in routine clinical care to evaluate decline in lung function in lung transplant patients. The University of Michigan (UM) has a standing Institutional Review Board (IRB) approved protocol that that allows for use of BAL fluid for research purposes. If clinical bronchoscopy has been performed within 6 weeks of screening, and no clinical indications of new infection are present (as determined by the principal investigator in consult with the treating pulmonologist), we will utilize the MSC results for this study. If bronchoscopy has not been performed, it may be done following screening and before enrollment, as an

optional part of this study. The informed consent document includes opt in/opt out language for bronchoscopy.

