5.8 Randomization

This is a randomized, double-blind, placebo-controlled multi-center study. Assignment to study treatment will be blinded to the study subjects, investigational site personnel, study vendors, and the Sponsor study team, except for the delegated personnel who will review and check the randomization and drug allocation for accuracy.

All patients will be randomized at the Baseline visit, using stratified block randomization with undisclosed block sizes. The stratification factor is FEV1 first vs concurrent FEV1 and FVC decline at time of CLAD onset. Our statistician, [name], will assist with randomization. She will provide the Research Pharmacy (via email) with randomization codes for two separate strata as mentioned above. Within each stratum the statistician will indicate treatment assignment"Active Pirfenidone" or "Placebo" and treatment label ID number. The Research Pharmacist (RP) will be told upon patient entry the stratum to which the patient belongs, identifying the appropriate randomization list for each patient. The RP will then dispense Active or Placebo based on the randomization code on the randomization list. The RP will refer to the randomization code at each dispensing.

In the event of a medical emergency in which breaking the blind is required to provide medical care to the subject, the investigator may obtain treatment assignment directly from the study statistician for that subject.

Visit	Screening ^A	1 Baseline	2 ^B +/- 7days	3 ^B +/- 7days	4 +/- 14day	5 ^B +/- 7days	6 ^B +/- 7days	7 EOT +/-	8 EOS +/-
					S			14day s	7days
Week	-6 - 0	0	4	8	12	16	20	24	28 ^c
Inclusion/exclusion criteria	х								
Informed consent	Х								
Randomization		Х							
Demographics	Х								
Vital Signs	Х	Х			Х			х	
Physical exam	Х	Х			Х			х	
Medical history	х	х							
Adverse events	х	х	Х	х	х	х	х	х	х
Non-elective hospitalizations		х	x	x	x	х	х	х	x
Medication Compliance			Х	х	х	х	х	х	
Concomitant medications	X	x	х	x	x	х	x	х	
Pregnancy test ^D		Х							
Standard of care labs	x	x	х	х	х	х	х	х	
including									
immunosuppressive									
drug levels									
Safety labs (LFTs) ^F	Х	Х	Х	Х	Х	Х	Х	Х	
Spirometry	Х				Х				
Full PFTs		Х						Х	
HRCT ^G		Х						Х	
EKG		Х			Х			Х	
Bronchoscopy with BAL ^H	x	x						х	
Vital status assessment									х

Table 1. Schedule of Assessments

A The time period between the screening and enrollment visit may be up to 6 weeks

B Weeks 4, 8, 16, 20: Laboratory testing may be performed locally

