C Week 28 visit may be performed as a telephone visit

D In women of child-bearing potential

E Immunosuppression drug levels will be collected and managed per standard of care

F LFTs will be monitored monthly

G HRCT may be done between screening visit and enrollment (visit 1)

H Results of BAL, if performed per standard of care, will be utilized as baseline if performed within the 6 weeks prior to baseline visit. Other bronchoscopies are optional.

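### Does the reuse of an earlier HRCT as baseline, worded differently in section 5.2 and Table 1 footnote G, need a change?

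*Combined protocol and SAP*

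**What the plan says.** Section 5.2 includes in the Visit 1 assessments: "Undergo an HRCT scan with inspiratory and expiratory image acquisition (if HRCT was not done in preceding 6 weeks"). It does not tie the earlier scan to screening or consent. Footnote G to Table 1 reads "HRCT may be done between screening visit and enrollment (visit 1"), and footnote A sets the outer limit: "The time period between the screening and enrollment visit may be up to 6 weeks". The first box of the study schematic, at the end of section 2, puts the HRCT among the steps before enrollment: "Screen potential subjects by inclusion and exclusion criteria; obtain medical history; HCRT, BAL (optional), vital signs".

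For lavage the plan is more explicit. Footnote H says "Results of BAL, if performed per standard of care, will be utilized as baseline if performed within the 6 weeks prior to baseline visit", and section 5.1 adds that there must be no sign of new infection.

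Section 4.4 looks back 28 days from enrollment for rejection ("Acute Rejection (AR) diagnosis by biopsy in the 28 days prior to enrollment") and for CLAD-directed therapies. It judges active pulmonary infection at enrollment. At screening, section 5.1 says "the consent form as well as inclusion and exclusion criteria will be reviewed".

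**The concern.** The scan is one of the two measurements that make up the primary endpoint, so its rule should be the same wherever it appears. Here the two places admit different scans, and the express permission given for standard-of-care lavage is absent for HRCT. The case could arise, because section 2 remarks: "While high resolution CT (HRCT) scans are routinely obtained at CLAD onset".

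The second worry is timing. A scan may be up to 42 days old, but the rejection and therapy exclusions reach back only 28 days. A patient scanned on day -42 and given pulse steroids on day -35 is still eligible on day 0. The measured fSAD change would then include the response to those steroids. Section 10.3 expects an SD below 9 partly because study scans are prospective and not taken from routine care; reusing routine scans would weaken that reason. At stake is precision, in a trial whose least favourable tabulated power is 48%.

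**Working it through.** **The plan's own figure.** Inputs from section 10.2: 30 per group, difference 9 - 4.5 = 4.5 points, SD 9. Two-sided 5% is assumed, since the documents do not state it. The standard error is 9 × √(2/30) = 2.324 and the noncentrality is 4.5/2.324 = 1.936. On 58 degrees of freedom the power is 47.8%, against the stated 48%. SD 7 and SD 5 give 68.7% and 92.9%, against 69% and 93%.

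**The two reuse rules.** Put screening at day -s, with s from 0 to 42.

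- Section 5.2 admits scans from day -42 to day 0.
- Footnote G describes scans from day -s to day 0.
- They coincide only at s = 42. With s = 14, scans from days -42 to -15 fall under section 5.2 but not under footnote G.

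Footnote G says a scan may be done in that interval; it does not exclude any other. The outer limit of six weeks is the same in both.

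**The 28-day comparison.** 42 - 28 = 14 days, namely days -42 to -29, lie before the look-back. Section 4.4 decides who may enter and does not say when the scan must be taken, so this is a gap and not a contradiction. A 28-day limit on reuse would close only part of it:

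- Pulse therapy on day -29 and a scan on day -28 would still be accepted, one day after treatment.
- A scan on day 0 after rejection on day -30 may also include recovery.
- Infection is judged only at enrollment, so a scan on day -10 is as exposed as one on day -35.

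What the limit would prevent is a non-excluded rejection or treatment falling between the scan and Visit 1.

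**Bias.** Section 5.8 randomizes at the baseline visit, so a reused scan is fixed before allocation. Disturbed baselines have the same distribution in both arms. With 20% of baselines shifted by 10 points, simulated type I error was 5.0% at SD 5, 7 and 9.

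**Variance from the longer interval.** Visit 7 has a window of ±14 days. The scan-to-scan interval is therefore 22 to 26 weeks with a day 0 scan, and can reach 26 + 6 = 32 weeks with reuse. At 9 points per 24 weeks, six extra weeks add 9 × 6/24 = 2.25 points. This happens before treatment in both arms, so the expected difference stays at 4.5. Assume a common slope and a lag uniform over 0 to 6 weeks:

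- SD of the lag effect: (6/√12) × 9/24 = 0.65 points.
- Total SD: √(81 + 0.65²) = 9.02.
- Power: 47.6%, a loss of 0.2 points.

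If every patient reused a day -42 scan, power would be 39.9% if SD grows as √(30/24) (SD 10.06), or 33.2% if it grows as 30/24 (SD 11.25). Those are extremes. Footnote G also permits a day -42 scan when screening is that early, so they do not measure the difference between the two rules.

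**Variance from unstable baselines.** If a share p of baselines is shifted by δ points, SD = √(SD₀² + p(1 - p)δ²). With p = 0.20:

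- δ = 10: SD 5 becomes √(25 + 16) = 6.40, power 76.3%; SD 9 becomes √(81 + 16) = 9.85, power 41.3%.
- δ = 5: SD 5 becomes √(25 + 4) = 5.39, power 88.9%; SD 9 becomes √(81 + 4) = 9.22, power 46.0%.

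Neither p nor δ comes from the documents. If everyone reused a scan, with timing uniform over 42 days, 14/42 = 33% would fall in days -42 to -29, and p = 0.20 would need 0.20/0.333 = 60% of those to be disturbed. If half reused scans, only 16.7% would fall there, so events confined to those days could not produce p = 0.20.

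**The case for a change.** The strongest opposing case is that clarity is cheap. The authors wrote an explicit rule for lavage, with an infection condition, and gave the primary-endpoint scan neither. One rule in two places would stop coordinators from applying different baselines, would require paired images, and would keep the baseline close to the state in which treatment starts. It would leave eligibility and visits as they are.

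The textual part stands: the plan does not say outright whether a pre-screening clinical scan may serve. But the staff running a single-center trial can settle that sensibly, and either answer gives a valid baseline. Pairing is already implied, because section 5.2 names both acquisitions and PRM (section 2) compares inspiratory with expiratory images; a scan without both gives no fSAD value.

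The precision argument is weaker. A 10-point shift exceeds the whole 9-point untreated change. SD 9 comes from routine-care scans, so adding such noise to it may count it twice. Section 10.2 already warns that power depends on the SD and tabulates 5 to 9. Section 6 recruits at any CLAD stage and counts 92 existing cases, so onset scans may often be older than six weeks; the documents do not give their timing.

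**Conclusion.** No change to the plan is needed. The wording of section 5.2 and footnote G is uneven, but the two can be read together, and no figure or analysis depends on the difference. The treatment comparison is unbiased because a reused scan is fixed before allocation. The effect on precision cannot be sized: the documents give no share of reused scans, no share taken in an unstable period, and no effect of such events on fSAD. Progression over the lag alone costs about 0.2 points of power at SD 9, assuming a common slope and a lag uniform over six weeks; larger losses need assumed shares and shifts, or every scan at the earliest permitted day.

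Moving from six weeks to 28 days is a trade-off: another CT for some patients against an unquantified gain that leaves recent treatment and infection only partly covered. Keeping six weeks is a fair choice.

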5.7 Early discontinuation

All subjects will be followed until study completion unless consent to do so is specifically withdrawn by the subject. If study treatment is discontinued, participants will be asked to continue with study assessments as planned including the HRCT at week 24 as per protocol.

5.8 Randomization

This is a randomized, double-blind, placebo-controlled multi-center study. Assignment to study treatment will be blinded to the study subjects, investigational site personnel, study vendors, and the Sponsor study team, except for the delegated personnel who will review and check the randomization and drug allocation for accuracy.

All patients will be randomized at the Baseline visit, using stratified block randomization with undisclosed block sizes. The stratification factor is FEV1 first vs concurrent FEV1 and FVC decline at time of CLAD onset. Our statistician, [name], will assist with randomization. She will provide the Research Pharmacy (via email) with randomization codes for two separate strata as mentioned above. Within each stratum the statistician will indicate treatment assignment"Active Pirfenidone" or "Placebo" and treatment label ID number. The Research Pharmacist (RP) will be told upon patient entry the stratum to which the patient belongs, identifying the appropriate randomization list for each patient. The RP will then dispense Active or Placebo based on the randomization code on the randomization list. The RP will refer to the randomization code at each dispensing.

In the event of a medical emergency in which breaking the blind is required to provide medical care to the subject, the investigator may obtain treatment assignment directly from the study statistician for that subject.

Visit	Screening ^A	1 Baseline	2 ^B +/- 7days	3 ^B +/- 7days	4 +/- 14day	5 ^B +/- 7days	6 ^B +/- 7days	7 EOT +/-	8 EOS +/-
					S			14day s	7days
Week	-6 - 0	0	4	8	12	16	20	24	28 ^c
Inclusion/exclusion criteria	х								
Informed consent	Х								
Randomization		Х							
Demographics	Х								
Vital Signs	Х	Х			Х			х	
Physical exam	Х	Х			Х			х	
Medical history	х	х							
Adverse events	х	х	Х	х	х	х	х	х	х
Non-elective hospitalizations		х	x	x	x	х	х	х	x
Medication Compliance			Х	х	х	х	х	х	
Concomitant medications	X	x	х	x	x	х	x	х	
Pregnancy test ^D		Х							
Standard of care labs	x	x	х	х	х	х	х	х	
including									
immunosuppressive									
drug levels									
Safety labs (LFTs) ^F	Х	Х	Х	Х	Х	Х	Х	Х	
Spirometry	Х				Х				
Full PFTs		Х						Х	
HRCT ^G		Х						Х	
EKG		Х			Х			Х	
Bronchoscopy with BAL ^H	x	x						х	
Vital status assessment									х

Table 1. Schedule of Assessments

A The time period between the screening and enrollment visit may be up to 6 weeks

B Weeks 4, 8, 16, 20: Laboratory testing may be performed locally

C Week 28 visit may be performed as a telephone visit

D In women of child-bearing potential

E Immunosuppression drug levels will be collected and managed per standard of care

F LFTs will be monitored monthly

G HRCT may be done between screening visit and enrollment (visit 1)

H Results of BAL, if performed per standard of care, will be utilized as baseline if performed within the 6 weeks prior to baseline visit. Other bronchoscopies are optional.

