11.2.1 Adverse Event Reporting Period

The study period during which all AEs and SAEs must be reported begins after informed consent is obtained and initiation of any study procedures and ends 30 days following the last administration of study treatment or study discontinuation/termination, whichever is earlier. After this period, investigators should only report SAEs that are attributed to prior study treatment.

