- Hospitalization or prolonged hospitalization required to allow efficacy measurement for the study or
- Hospitalization or prolonged hospitalization for scheduled therapy of the target disease of the study.

e. Pregnancy

If a female subject becomes pregnant while receiving the study drug or within 30 days after the last dose of study drug, a report should be completed and expeditiously submitted to Genentech, Inc. Follow-up to obtain the outcome of the pregnancy should also occur. Abortion, whether accidental, therapeutic, or spontaneous, should always be classified as serious, and expeditiously reported as an SAE. Similarly, any congenital anomaly/birth defect in a child born to a female subject exposed to the study drug should be reported as an SAE.

Additional information on any pirfenidone exposed pregnancy and infant will be requested by GenentechDrug Safety at specific time points (i.e. after having received the initial report, at the end of the second trimester, 2 weeks after the expected date of delivery, and at 3, 6, and 12 months of the infant's life).

f. Post-Study Adverse Events

The investigator should expeditiously report any SAE occurring after a subject has completed or discontinued study participation if attributed to prior {study drug} exposure. If the investigator should become aware of the development of cancer or a congenital anomaly in a subsequently conceived offspring of a female subject who participated in the study, this should be reported as an SAE.

g. Reconciliation

The Sponsor agrees to conduct reconciliation for the product. Genentech and the Sponsor will agree to the reconciliation periodicity and format, but agree at minimum to exchange quarterly line listings of cases received by the other party.

If discrepancies are identified, the Sponsor and Genentech will cooperate in resolving the discrepancies. The responsible individuals for each party shall handle the matter on a case-by-case basis until satisfactory resolution. The sponsor shall receive reconciliation guidance documents within the 'Activation Package'.

h. AEs of Special Interest (AESIs)

AEs of Special Interest are defined as a potential safety problem, identified as a result of safety monitoring of the Product

For this study, there are no AESIs.

I. Adverse Event Reporting

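### The last scheduled safety call is fixed at week 28 and not tied to the last dose, so for patients treated to about week 24 it can fall before the 30-day adverse event period ends

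*Combined protocol and SAP*

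**What the plan says.** Section 11.2.1 starts the AE and SAE reporting period after consent. The period "ends 30 days following the last administration of study treatment or study discontinuation/termination, whichever is earlier". It continues: "After this period, investigators should only report SAEs that are attributed to prior study treatment". Section 11.3.2(e) uses the same length for pregnancy, which is reportable if it occurs on study drug "or within 30 days after the last dose of study drug".

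The visits are timed by study week. Section 5.5 and Table 1 put Visit 7, labelled end of treatment, at week 24 with a window of +/-14 days. Its tasks include: "Collect unused study medication and return to investigational pharmacy". Section 5.6 and Table 1 put Visit 8, labelled end of study, at week 28 with a window of +/-7 days. At that call the coordinator reviews hospitalizations and adverse events and collects vital status. Footnote C to Table 1 concerns only how the contact is made: "Week 28 visit may be performed as a telephone visit". No section ties Visit 8 to the last dose, sets a minimum interval after Visit 7, or schedules anything later.

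On patients who stop treatment early, section 5.7 says: "If study treatment is discontinued, participants will be asked to continue with study assessments as planned".

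**The concern.** The protocol states one length for the reporting period and a visit schedule that does not deliver it. The mismatch needs no deviation: a patient who completes treatment and attends both visits on the planned dates has the last scheduled contact before day 30. From that call until day 30, an event is recorded only if the patient volunteers it or the centre happens to learn of it.

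Safety is among the secondary endpoints. Section 4.1 counts subjects with treatment-related adverse events, and section 10.1 counts subjects with one or more SAEs. Neither count carries its own time limit, so the reporting period in section 11.2.1 is the natural cut-off. Active follow-up within that period would be complete for some patients and cut short for others, depending on where the two visits fall in their windows.

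**Working it through.** **Inputs**
- Reporting period: 30 days after last administration (section 11.2.1). This is a stated rule, so there is no plan figure to reproduce.
- Visit 7: week 24, +/-14 days. Visit 8: week 28, +/-7 days (sections 5.5 and 5.6; windows from the Table 1 header, whose layout is broken in the text but readable).
- Baseline (week 0) is counted as day 0.

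**Calendar days**
- Visit 7: 24 x 7 = day 168, window 154 to 182.
- Visit 8: 28 x 7 = day 196, window 189 to 203.

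Interval = day of Visit 8 - day of last dose. Shortfall = 30 - interval, where positive.

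**Case A: both visits on time, last dose on day 168.** 196 - 168 = 28 days. Shortfall 30 - 28 = 2 days.

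**Case B: last dose on day 168, Visit 8 anywhere in its window.** The interval runs from 189 - 168 = 21 to 203 - 168 = 35 days. The largest shortfall is 30 - 21 = 9 days. Day 168 + 30 = 198, so a call on days 189 to 197 is early (9 of the 15 permitted days) and a call on days 198 to 203 is not.

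**Case C: dosing continues to Visit 7, whenever it is held.** This is an assumption, suggested by the end-of-treatment label and by drug collection at that visit, but not stated. The interval runs from 189 - 182 = 7 to 203 - 154 = 49 days. The largest shortfall is 30 - 7 = 23 days, or 23/30 = 77% of the period. Of the 29 x 15 = 435 in-window day pairs, 240 (55%) give fewer than 30 days. That counts combinations and does not forecast patients.

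**Which last-dose days are covered**

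| Last dose | Coverage by an in-window Visit 8 |
|---|---|
| Day 159 or earlier (189 - 30) | Always at least 30 days |
| Days 160 to 173 (203 - 30 = 173) | Depends on the date of the call |
| Day 174 or later | Never 30 days |

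An early stopper who stays on the visit schedule and whose last dose is on or before day 159 is therefore fully covered. The shortfall concerns patients treated to about week 24.

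**The case against.** The best counter-argument lies in the closing words of the rule in section 11.2.1, under which the earlier of two events governs. If reaching Visit 8, labelled end of study, counts as study discontinuation or termination and itself closes the period, no reportable days follow the call and the conflict disappears. That reading is possible but less natural. The sentence reads more easily as 30 days after whichever event comes first, which for a completer is the last dose. The other reading would mean that an on-time completer never reaches the 30 days stated. The text needs to say which is meant.

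Several limits do stand:
- The 23-day shortfall needs a Visit 7 at the late edge, a Visit 8 at the early edge, and dosing up to the late Visit 7. The synopsis gives treatment over 24 weeks, and nothing says dosing runs past that when the visit is late.
- Section 11.2.2 has volunteered events, and those detected by any other means, reported. Attributed SAEs remain reportable after the period (sections 11.2.1 and 11.3.2(f)). The synopsis also describes patients as cared for at the transplant centre without loss to follow-up.
- Footnote C gives only the mode of contact. The conflict rests on sections 5.6 and 11.2.1 and the Table 1 header.

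A reader might go further and infer that safety comparisons between arms are biased, or that 30-day vital-status counts will be incomplete. The documents support neither. Both blinded arms share one schedule, and no stopping rates by arm are given from which a difference could be estimated. Vital status is collected at week 28, and no 30-day vital-status count is defined. Treatment intolerance is counted over 24 weeks and discontinuation before 24 weeks, so neither depends on the days after Visit 8.

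**Conclusion.** The point holds as a minor inconsistency between the visit schedule and the reporting rule. For patients treated to about week 24, the last scheduled contact is 2 days short of 30 when everything is on time, and up to 9 days short if the last dose is on day 168. The figure of up to 23 days applies only if dosing continues to a late Visit 7, and it is an extreme, not a typical value.

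What is at risk is active collection, in completers, of non-serious AEs, SAEs not attributed to treatment, and pregnancies within 30 days of the last dose. It would be too strong to say that such events are lost or cannot be reported. The primary fSAD endpoint and the sample size are untouched. The conclusion assumes that the 30 days run from the last dose for completers, the more natural reading of section 11.2.1.

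**What to change.** Reconcile sections 5.6 and 11.2.1 and Table 1:

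1. If the 30-day period stands as written, schedule the Visit 8 phone call at week 28 or at least 30 days after the last dose, whichever is later. Set its window so that the call cannot be made earlier than 30 days after the last dose.
2. State in section 11.2.1 whether end of study counts as study discontinuation or termination, and whether the 30 days run from the earlier event or are cut off by it.

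The later-of-two rule matters. Counting Visit 8 from the last dose alone would bring end of study forward for early stoppers, possibly ahead of the week 24 HRCT that section 5.7 asks them to attend.

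The cost is small: wording in Table 1 and two sections, with no added visit or procedure, and the contact can remain a phone call. For an on-time completer it moves 2 days, to day 168 + 30 = 198. For early stoppers covered by week 28 it stays at day 196. In the extreme of a last dose on day 182 it falls on day 212, 9 days after the latest day now permitted (203). Vital status would then be collected slightly after week 28 for some patients, so the date of the call should be recorded with it.
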